Thanks to its branched structure That Confers ITS prebiotic effect at the same time it is classified That as soluble fiber, Which is fermented in the colon by bacteria endogenous, giving rise to metabolic and energetic substrates. Due to ITS osmotic potential and Its excessive fermentation, some secondary effects Caused by ITS Intakes are flatulence, meteorism, abdominal pain and discomfort, as well as diarrhea^{17,18}.

It has-been associated in vitro and in vivo preliminary studies, with the Increase bifidobacteria and lactobacillus of the population When They are Compared with a placebo. In the same way, there is a trend of

Presenting an improvement in the consistency of evacuations, as well as a decrease in the feeling^{19,20} constipation.

It has-been associated in vitro and in vivo preliminary studies, with the Increase bifidobacteria and lactobacillus of the population When They are Compared with a placebo. In the same way, there is a trend of presenting an improvement in the consistency of evacuations, as well as a decrease in the feeling^{21,22} constipation.

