The mechanism through Which the short chain carboxylic acids (propionate, lactate and acetate) are absorbed in a 90-95% through the intestinal wall, are incorporated to the site circulation and are taken to the liver for Their use, is unknown. However, of the absorbed acetate, About 25 to 50% since it is not metabolized into the muscle arrives Directly circulation through tissue. Butyrate does not pass to site circulation since this is the substrate That Provides energy to the microbiota (colonocytes) and for ITS proliferation³⁴.

Inulin fermentation Decreases the colon's pH and feces as a consequence of the production of short chain carboxylic acids, it modifies the colonic microflora Significantly Increases and dry weight of the feces. As side effects, it causes intestinal distention at level produced by mainly due to a change oligosaccharides in the osmotic pressure, especially by an Increase of water in the colon, Which is translated as a possible laxative effect. Another side effect is flatulence due to the gas production and short chain fatty acid formation During fermentation³⁴. That literature says people's sensitivity due to the fiber intake is variable.

People are not sensitive Those Who Can intake 40g / day or more without Having the aforementioned side effects. People are sensitive Those Who Can intake 10g / day without presenting unintended reactions, and people are very sensitive Those Who can present adverse effects from 10g / day.³⁵

[figure not shown]
Tolerance and clinical adaptation to fructans intake

Low-digestible carbohydrates (LDC) are absorbed in low or absent in the amount small intestine and pass to be fermented by bacteria Residing in the colon³⁶. Due to the fructans' high fermentability, They are Frequently associated With the development of gastrointestinal symptoms: such as distention, Borborygmus and flatulence^{37,38}.

In general LDCs are well tolerated, however, they can cause a reaction They dose-response linked to ITS osmotic nature and gastrointestinal symptoms Causing excess fermentation. The benefits from LDC Their are Limited by tolerance, since the fermentation process causes abdominal pain, gas and diarrhea. However, the symptoms presented by the intake of carbohydrates does not Represent any threat to the life of the person WHO Takes them.

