7. To evaluate- gastrointestinal transit in Patients With functional constipation and after ingestion of before blue agave Tequilana Weber fructans.

8. Methodology: General Design.

Describes the overall design of the study and, if relevant, specify the following points:

- a) Study design: Describes if it is randomized / non-randomized, controlled, cohort, Blinding type (double-blind, single), type of controls (placebo, active medication), wash period.
- b) Maneuver or intervention description.
- c) Sample size (# of Patients to be included; justify the calculation)
- d) Treatment allocation mechanism (random / open)
- e) Treatment groups and
- f) Duration of Individual follow-up

Study Design

This is a prospective, randomized, controlled and single blind study to determine the phase III efficacy of the blue agave fructans Tequilana Weber intake in subjects with functional constipation.

In order to Achieve so, it is planned to include over 18 years of Patients age Fulfill the WHO as well as inclusion criteria The Rome III criteria for functional constipation. (See table below) 2.

The phase of our study is designated based on article 66 of chapter II "On Pharmacological Research" of the Regulation of the General Law on Health in Research That defines PHASE III studies Follows as: It is the administration of a research drug to large groups of Patients (Usually external), to define ITS therapeutic utility and identification identify adverse reactions, interactions and external factors That May alter the pharmacological effect.

ROME III criteria

To Comply with the presence of symptoms for more than 6 months before diagnosis, Having Said symptoms for at Least 3 consecutive months or not, and:

1. Absence of abdominal pain or discomfort in the last 3 months.
2. Include 2 or more of the following symptoms.
 - Excessive effort in more than 25% of the evacuations.
 - Hard stool or "pellets" in more than 25% of evacuations.
 - Sensation of incomplete evacuation 25% of evacuations.
 - Sensation of blockage or blockage in 25% evacuations.
 - Maneuvers to Facilitate expulsion in 25% of evacuations.
 - Less than 3 evacuations per week.
3. Stool consistency decrease, rarely, without the use of laxatives.
4. Insufficient criteria of IBS.

Patients of the institute will be called after invitations to Participate in Placing a protocol for Patients With constipation. Patients Who Have Not Been registered and meet the inclusion criteria May Also Participate.

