spontaneous evacuation It is defined as an evacuation in the absence of use of laxatives, suppositories or enemas and complete evacuation is defined as spontaneous evacuation to that sensation of incomplete emptying of the rectal ampulla.

secondary measured variables:

- I. Effect of supplementation of fructan Weber blue agave Tequilana in the form of bowel movements, assessed by the Bristol scale. It is defined as a change in the form of evacuations when presenting a change in the classification of Bristol, more than 50% according to the daily evacuations taking the average of the evacuations submitted within 15 days.

- II. Effect of supplementation of fructan Weber blue agave Tequilana in the frequency of bowel movements. It shall be defined as responder presenting increased 50% in stool frequency compared with baseline, according to the daily bowel movements taking the average of evacuations presented at 15 days.
- III. Evaluate the impact of the concentration of short-chain fatty acid, particularly butyrate, in the feces of subjects before and after addition of fructans Tequilana Weber blue agave. The butyrate concentration was determined by method of gas chromatography and the increase will be assessed in millimoles per liter.
- IV. Evaluate the impact of supplementation fructans Weber blue agave Tequilana the microbiota by determining edges present in feces of the subjects before and after the supplementation fructan derivatives fiber; which are:
 - 1) **Actinobacterias** (Bifidobacteriales)
 - 2) **Bacteroidetes** (Prevotella, Paraprevotela, Ruminococcaeaceae, Faecalibacterium)
 - 3) **Firmicutes** (Veillonella, Anaerostipes, lactobacilli Clostridiales, Enterococcus)
 - 4) **Proteobacteria** (Bilophila, Escherichia).
 - 5) **Euryarchaeota** (Methanobacteriales)
- V. To evaluate the impact of serum glucose concentration and HbA1c fasting serum of subjects before and after addition of fructans Tequilana Weber blue agave. HbA1c concentration is determined as it is intended to monitor the impact of fiber on glucose throughout the duration of the study (2 months) and in order to avoid the variability that fasting glucose.

Gas Chromatography: (determination of short-chain fatty acid AGCC)

AGCC for determining ion detector flame will be used. The following steps are performed:

1. ethylbutyrate - 1 g of faeces which is added 50 uL of 2 homogenizará.
2. 1 mL of hydrochloric acid was be added.

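### A more-than-50% change in the 15-day mean Bristol type can be met by a minority of loose stools among unchanged hard ones, and is missed by uniform one-step softening

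*Combined protocol and SAP*

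**What the plan says.** In section 10 (Methodology: Outcomes and variables), secondary variable I concerns the form of bowel movements on the Bristol scale. "It is defined as a change in the form of evacuations when presenting a change in the classification of Bristol", and the amount of change is "more than 50% according to the daily evacuations taking the average of the evacuations submitted within 15 days". The definition gives no direction, target range of types, upper limit or rule for loose stools. It is also not restricted to spontaneous evacuations, a term that the same section defines for the primary outcome.

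Secondary variable II, directly below, uses the same 15-day average and defines a "responder presenting increased 50% in stool frequency compared with baseline".

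On side effects, the agave part of section 6 (Theoretical framework) says "some secondary effects Caused by ITS Intakes are flatulence, meteorism, abdominal pain and discomfort, as well as diarrhea". The subsection on tolerance and adaptation to fructans says of low-digestible carbohydrates that "the fermentation process causes abdominal pain, gas and diarrhea", and describes a dose-response reaction linked to their osmotic nature.

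For entry, the Rome III list in section 8 says "Include 2 or more of the following symptoms". Hard stool in more than a quarter of evacuations is one of the six symptoms listed.

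**The concern.** Bristol types are ordered classes, with the abnormal forms at the two ends and the normal ones in the middle. A mean over such a scale cannot tell a patient with normal stools from one with mostly hard and some watery stools. A percentage change in that mean adds a second problem: the size of a one-step improvement depends on where the patient starts.

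If loose stools are more common in one arm, the form endpoint could credit that arm with efficacy for what is really a tolerability effect. Two comparisons are exposed: agave against psyllium, and 5 g against 10 g, where secondary objective 1 sets out to compare efficacy and tolerability side by side. With 15 patients planned per arm, each misclassified patient moves an arm's responder rate by 1/15 = 6.7 percentage points.

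**Working it through.** The documents state no figure derived from this endpoint, so there is none to reproduce. The check is whether the rule classifies simple stool patterns sensibly.

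**Inputs**
- Threshold: a change of more than 50% in the 15-day average (section 10, variable I). That the comparison is with the patient's own baseline mean is read across from variable II.
- Scale: types 1 (hardest) to 7 (watery), with 6 and 7 loose. This is an assumption about the instrument; the protocol does not list the types.
- Baseline mean type *b*: not given. A range of 1.5 to 3.5 is shown.

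**Loose stools with all else unchanged.** Let a share *p* of stools be of loose type *L* and let the rest stay at mean type *b*. The new mean is (1 − p)b + pL = b + p(L − b). It exceeds 1.5b when

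p > 0.5b / (L − b).

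| Baseline mean *b* | Share of type 7 needed | Share of type 6 needed |
|---|---|---|
| 1.5 | 0.75/5.5 = 13.6% | 0.75/4.5 = 16.7% |
| 2.0 | 1/5 = 20% | 1/4 = 25% |
| 2.5 | 1.25/4.5 = 27.8% | 1.25/3.5 = 35.7% |
| 3.0 | 1.5/4 = 37.5% | 1.5/3 = 50% |
| 3.5 | 1.75/3.5 = 50% | 1.75/2.5 = 70% |

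A minority of loose stools is enough throughout the range of clearly hard baselines. It stops being enough at *b* = 3 for type 6 and at *b* = 3.5 for type 7.

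**Example.** At baseline all stools are type 2 (mean 2.0). On treatment there are seven stools of type 2 and three of type 6: (7 × 2 + 3 × 6)/10 = 3.2, and 3.2/2 − 1 = +60%. The rule is met with 70% of stools still hard.

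**Uniform improvement by one type**
- All stools from 1 to 2: +100%, met, although every stool is still hard.
- All stools from 2 to 3: 3/2 − 1 = +50%, which is not more than 50%, so not met.
- All stools from 3 to 4: 4/3 − 1 = +33%, not met.

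The rule therefore errs in both directions. Specifying an upward direction would not help, because the false responses above are already upward changes.

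**The case against.** The strongest objection is to the reading. The sentence is loosely worded and could mean that more than half of the evacuations change class. A minority of loose stools could not then qualify. This stands as a limit on the finding. But the reference to taking the average would then have little function, and variable II uses the same average for a change from baseline. Even on that reading a diarrhoeal majority would count, because no direction or target is set.

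The shares also rest on assumed baselines and on all other stools staying unchanged. Since hard stool is only one of six optional entry symptoms, some patients may start at a mean of 3 or more. This stands too, and is why a range is shown. A reader might infer a general statement that responders could still have some three-quarters or more of their stools hard. That holds only for the lower baselines (*b* of 2 or less), not for *b* = 2.5. Nor does a minority suffice at every threshold: with a 100% threshold, *b* = 2 and type 6, the share must exceed 2/4 = 50%.

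A reader might also infer that the endpoint is biased toward agave or toward the higher dose. The documents do not support that. They name diarrhoea but give no rate, and several statements point the other way:
- Signs of intolerance are placed at intakes above 20–30 g (subsection on toxicology).
- Regular intake is said to reduce diarrhoea (subsection on tolerance).
- In the table of agave studies, one study reports better stool consistency at 7.5 g, one reports no adverse effects at 7.5 g, and one reports no difference in consistency at 5 g.

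Finally, adverse effects are recorded on a separate sheet, so diarrhoea need not go unseen. That does not repair the form score.

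**Conclusion.** The concern holds for this secondary endpoint, on the reading of variable I as a change in the 15-day mean type. This is more than a missing detail: the rule as stated counts some patients with mostly unchanged hard stools as changed in form, and rejects some whose every stool softened by one type. The loose-stool share that triggers it is about 14–17% at a baseline mean of 1.5, 20–25% at 2 and 28–36% at 2.5. These figures rest on the assumed Bristol numbering and on the other stools being unchanged.

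What is shown is a mechanism. It could distort the between-arm and between-dose comparisons of form; how often, and in whose favour on balance, cannot be worked out from the documents. The primary outcome and the sample size do not use this variable.

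**What to change.** Do not use percentage change in the mean Bristol type. From the evacuation diary already kept, derive for each patient and each 15-day window the share of hard evacuations (types 1–2) and, separately, of loose evacuations (types 6–7). Compare the change in hard share between arms, and report the loose share as tolerability. The two need to be read together: in the example above the hard share falls from 100% to 70% only because 30% of stools became loose.

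If a responder definition is kept:
- base it on these shares and state the direction;
- have the sponsor fix the cut-offs before analysis. The 25% hard-stool figure in the Rome III list is one available anchor, although it is an entry symptom and not a response criterion. The documents offer no source for a loose-stool limit, so that is the sponsor's choice;
- state how patients without a raised hard share at baseline are handled;
- state whether evacuations after rescue laxatives count.

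The cost is a reworded variable and a new derivation from data already being collected. A reader might expect the responder rate to fall, but it may move either way: a patient going from all type 2 to all type 3 fails the present rule, yet would have a hard share falling from 100% to 0%.

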The study to be Carried out will be Explained and read and, where appropriate, the informed consent will be signed by the Patient During the initial visit (Visit 1) of eligibility, Where the subject will be Given 2 questionnaires (see annexes), one They meet to determine if the ROME III criteria for functional constipation (FC) and another to ASSESS if the patient does not meet the criteria for irritable ROME III bowel syndrome (IBS) and a baseline breath test will be performed.

Having met the inclusion criteria, the patient will be EVALUATED by a graduate in nutrition with the objective of Evaluating the fiber intake in the subject's usual diet. The amount of daily fiber intake will be standardized and a diary will be Given to Evaluate Said intake (see annexes) as well as a diary Where the subject will keep a record of his / her evacuations (see annexes).

In Addition, the previous use of fiber supplements and laxatives, which must be suspended at Least 2 months prior to randomization, will be EVALUATED.

The subject will return to a second visit (Visit 2) (Which will depend on Whether the patient is taking laxatives or fiber supplements) for a complete physical evaluation and the fiber intake diary will be Assessed to determine the amount of fiber intake in the diet as well as the diary of evacuations and the SmartPill © will be Given and That way, the patient will return to the hospital to register the data after the capsule Having evacuated.

The patient will return a week later (Visit 3) on a 12 hour fast, the fiber intake and the evacuation diaries will be re-EVALUATED and will be EVALUATED They again by a nutritionist. A new breath test will be Carried out. The subject will be

Asked to complete the SF-36 Quality of Life Questionnaire. A stool sample will be Collected for ITS analysis in Addition to a blood sample for determination of fasting glucose, glycosylated hemoglobin A1c, Insulin and full lipid profile.

The subjects will be randomized to receive one of four treatments That can be Psyllium plantago 15g, blue agave Tequilana Weber fructans at doses of 5, 10g and blue agave Tequilana Weber fructans at a dose of 5 g + 10 g excipient for a concentration of 33 % of blue agave fructans Tequilana Weber.

The randomization will be computer-generated with a participation number and the assignment of the treatment will be consecutive.

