- functional constipation ROME III criteria as
- Subjects ≥55 years with recent colonoscopy (<3 years)

b) Exclusion criteria

- Taking supplements of fiber in the last 2 months
- Stimulant laxatives consumption chronically (Senna, Bisacodyl)
- decompensated comorbidities (example: uncontrolled diabetes mellitus HbA1c > 9%, decompensated Organ failure, decompensated hypertension (untreated or TA > 160 mmHg systolic and 95 mmHg diastolic)

- Using digital maneuvers or enemas to achieve evacuation
- Personal history of active or previous cancer
- abdominal surgery (except appendectomy, cholecystectomy, hysterectomy)
- Presence of alarm data in the last 6 months (trans-rectal bleeding, unexplained weight loss, abdominal pain)
- Use of drugs known promote constipation (opioid derivatives, clacioantagonistas, anticholinergics tricyclic antidepressants type)
- Prostration (immobility or poor mobility)
- Diseases such as untreated hypothyroidism with hormone replacement, and diseases associated with hypercalcemia that promote constipation
- Other causes of secondary constipation
- Meet criteria for constipation predominant irritable bowel
- Pregnancy.

c) Elimination criteria (considering pregnancy if necessary).

- Requiring individuals to withdraw their informed consent
- acute illness (eg appendicitis, medical-surgical requiring hospitalization intervention and follow-up)
- In our study provides no substitute for patients who have completed or prematurely abandoned the study. It is contemplated an analysis by intention to treat and the percentage of losses for each treatment group will be collected, clarifying the reason why the study was abandoned.

10. Methodology: Outcomes and variables

a) Variables / Main outcome measure

b) Variables / secondary endpoints measured

b) frequency measurements,

c) Criteria for success and failure, and if necessary

d) Strategy statistical analysis.

Where applicable should be specified and substantiated techniques, equipment and / or instruments to be used in the measurement (this includes mechanical / electronic / cyber special equipment, evaluation forms, questionnaires, matching tables, etc.), indicating the validity criteria , reproducibility and quality controls that are the same.

main outcome variable:

Effect of supplementation of fructans Tequilana Weber blue agave in increasing at least one complete evacuation from basal spontaneous.

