Sequencing and analysis of the amplified fragments is by fluorescent sequencing equipment terminator 3130 / genetic analyzer (Applied Biosystems).

The PCR products were sequenced and analyzed and will be submitted to GenBank for species identification.

Extracting bacterial DNA and quantitation of bacterial species used to demonstrate the prebiotic effect of agave fiber, since selective growth of the population of bifidobacteria and lactobacilli and occurrence of short-chain fatty acid in stool is expected.

Thus in addition to the functional properties and their effects on constipation, you may check the prebiotic effect of agave fructans.

Data analysis:

a) Statistical analysis plan

The data obtained will be analyzed with SPSS version 24. For continuous variables the results are presented in mean ± standard deviation when the variables are normally distributed or medians and percentiles otherwise and as frequency and percentages when they were categorical. For basal and subsequent comparison to the intra intervention groups, Student's t-test for paired samples (variables with normal distribution) or the Mann-Whitney U (variables without normal distribution) is used in the case of continuous variables and X² or the McNemar test in the case of categorical variables. For comparison between groups ANOVA (variables with normal distribution) or Kruskal-Wallis (non-normal distribution variables) used for continuous variables and the same percentage of change obtained when the variables are continuous.

Also an analysis of covariance (ANCOVA) was performed to control variables that might have an effect on the response variables.

b) Non-inferiority study

There are multiple fibers on the market that are promoted as beneficial supplement to patients with constipation; Despite this, there is insufficient scientific evidence from randomized controlled trials to support its use. Psyllium psyllium, is the first-line treatment used for such functional bowel disorder; fructans tequilana Weber blue variety are soluble fibers which are rich fructooligosacáridos role in prebiotic substance with the which is associated with a number of health benefits including intestinal health; therefore, as an alternative treatment in patients with constipation using these fructans it is raised to generate clinical evidence and demonstrate the therapeutic potential similar to plantago psyllium.

c) Sample size

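### Secondary variable II defines response only as a 50% rise over the patient's own baseline: it can credit patients still under 3 evacuations a week, miss others who cross that line, and is undefined at a zero baseline

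*Combined protocol and SAP*

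**What the plan says.** Section 10 lists two secondary variables taken from the evacuation diary.

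- **Variable II, frequency:** "It shall be defined as responder presenting increased 50% in stool frequency compared with baseline", "taking the average of evacuations presented at 15 days". This is the whole rule.
- **Variable I, form:** the form counts as changed on "a change in the classification of Bristol, more than 50% according to the daily evacuations", again averaged over 15 days. The sentence mentions neither a baseline nor a responder, and gives no direction and no target range.

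Three other places bear on these rules.

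- **Section 8, ROME III criteria.** The entry instruction is "Include 2 or more of the following symptoms". One of the six symptoms listed is "Less than 3 evacuations per week", so low frequency is one route into the trial but is not required.
- **Section 10, main outcome.** This uses an absolute step, "increasing at least one complete evacuation from basal spontaneous", with no time unit.
- **Data analysis, item a.** Groups are compared by ANOVA or Kruskal-Wallis on continuous variables and on "the same percentage of change obtained when the variables are continuous". An ANCOVA is also mentioned, but no covariate is named.

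The period that supplies the baseline frequency is not stated. Section 8 hands out the evacuation diary at Visit 1 and reviews it at Visit 2 and again at Visit 3, one week after Visit 2.

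**The concern.** A purely proportional rule sets a different hurdle for each patient. At low baselines a small gain is enough. At higher baselines the hurdle can lie above anything that constipation treatment aims for: since entry does not require low frequency, a patient entering at 7/week would have to reach 10.5/week. The rule therefore does not line up with the protocol's own frequency criterion, nor with the absolute step in its main outcome.

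A ratio of two small counts is also noisy. Some patients will meet a 50% rise with no change in their true rate, and a patient with no baseline evacuations has no ratio at all. Chance responders arise in every arm, so they inflate each arm's response rate and dilute contrasts between arms. That matters in a trial whose stated aim is to show an effect similar to psyllium with only 15 patients per arm.

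The Bristol rule raises a related question: what a 50% change in an ordinal stool class means, and whether it corresponds to a normal stool.

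**Working it through.** The plan gives no expected response rate for either rule, so there is no plan figure to reproduce.

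**1. The frequency rule against the 3/week line.** The threshold is 1.5 × baseline, reading the rule as at least 50%.

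| Baseline/week | Needed/week | Example | Change | Responder? | Follow-up at or above 3/week? |
|---|---|---|---|---|---|
| 1.0 | 1.5 | 1.5 | +50% (+0.5) | yes | no |
| 1.9 | 2.85 | 2.85 | +50% (+0.95) | yes | no |
| 2.0 | 3.0 | 3.0 | +50% (+1.0) | yes | yes |
| 2.5 | 3.75 | 3.5 | +40% (+1.0) | no | yes |
| 2.9 | 4.35 | 4.3 | +48% (+1.4) | no | yes |
| 5.0 | 7.5 | – | – | – | at or above at entry |
| 0 | undefined | – | – | – | – |

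Since 1.5 × b < 3 exactly when b < 2, response while still below 3/week is possible at every non-zero baseline below 2/week. Crossing 3/week without responding is possible only for baselines between 2 and 3/week. A change from 1 to 3/week (+200%) does count.

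**2. Chance response with no true change.** Assumptions, none of them from the documents: baseline count B and follow-up count F are independent Poisson with the same weekly rate r, over w_b and w_f weeks. Zero baselines are set aside as undefined.

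P = Σ_{k≥1} Pr(B = k) · Pr(F ≥ 1.5·k·w_f/w_b) / Pr(B ≥ 1)

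Follow-up is 15 days (w_f = 15/7). Since the baseline window is not stated, two are shown.

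| True rate/week | 15-day baseline | 1-week baseline |
|---|---|---|
| 1 | 31% | 10% |
| 2 | 30% | 24% |
| 3 | 26% | 28% |
| 5 | 19% | 26% |
| 7 | 15% | 21% |

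Undefined results at 1/week: exp(−15/7) = 0.117, or 12%, with a 15-day baseline; exp(−1) = 0.368, or 37%, with one week.

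More regular bowel habits (gamma-distributed intervals, shape 2 and shape 4, 15-day windows) give 32% and 32% at 1/week, 25% and 18% at 2/week, and 7% and 2% at 7/week.

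**3. The Bristol rule.** Two readings are possible.

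- *Percentage change in the mean score from baseline.* The threshold is above 1.5 × baseline. A move from 1 to 2 (+100%) counts, 2 to 3 (exactly +50%) fails, 3 to 4 (+33%) fails, and a baseline of 4 must exceed 6.
- *A changed class in more than half of evacuations.* These thresholds disappear and 3 to 4 counts. So does 1 to 2, and so does a change in either direction.

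Neither reading refers to a normal stool range.

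**4. What the alternative buys.** An illustrative Poisson simulation of two arms of 15, baselines spread over 1 to 7/week, 15-day windows and a true difference of +1.5/week gave about 58% power for baseline-adjusted change. Comparing +50% responder proportions by an exact test gave about 18%. An uncorrected chi-square test raises the responder figure to roughly 30%, which narrows the gap but does not close it.

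**The case against.** The strongest reply is that these are secondary variables. The main outcome already uses an absolute gain, and the analysis plan already provides for continuous comparisons and an ANCOVA. That limits the importance of the point but does not remove it. The ANCOVA sentence names neither baseline frequency nor variable II, it does not replace the written responder rule, and the same paragraph adds percentage change, which also fails at a zero baseline.

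The reply is right against four stronger readings that a reader might infer.

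- **That both rules demand a 50% change from the patient's own baseline.** Variable I names no baseline and may mean a class change in over half of stools. Only its ambiguity and lack of a target range are established.
- **That normalised patients generally fail to respond.** For frequency this is confined to baselines between 2 and 3/week.
- **That low-baseline patients respond by chance most often.** This depends on an unstated window. With a one-week baseline the figure at 1/week is the lowest of those shown.
- **That response rates would reflect the baseline mix rather than benefit.** Take the 15-day Poisson rates above and an equal mix of 1, 2, 3, 5 and 7/week. The SD of those rates is about 0.062, so baseline mix adds 0.062 × √(2/15), about 2 percentage points, to the SD of a difference between two arms of 15. Ordinary sampling error is √(2 × 0.243 × 0.757/15), about 16 points. Randomised arms share the same mechanism, so it dilutes the comparison and does not favour one arm.

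**Conclusion.** The point holds for variable II. That a patient can respond below 3/week, or cross 3/week without responding, is arithmetic from the protocol's own rule and its own criterion, as is the undefined result at zero; none of this needs an assumption. The chance-response figures do: they assume Poisson counts or gamma-distributed intervals, no treatment effect and a chosen baseline window. Over the Poisson cases they span 10% to 31%, and more regular habits bring them down to 2% at 7/week. They show that the rule is noisy, not how noisy it will be in this trial.

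For variable I the finding is narrower: the definition can be read in two ways that classify the same patient differently, and neither is anchored to a normal stool.

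The main outcome is untouched. This is a change that should be made to two secondary definitions; it is not a threat to the trial's main conclusion.

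**What to change.** **Variable II.** Replace the +50% responder rule and the percentage-change comparison with the between-arm difference in weekly evacuation frequency over the 15-day window. Use all patients, with baseline frequency as the named ANCOVA covariate. State which diary days form the baseline and which 15 days form the follow-up. Zero baselines then need no special treatment. If a +50% rate is still wanted, report it descriptively only and say how zero baselines are counted.

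An obvious substitute, at least 3/week with a rise of at least 1/week among patients starting below 3/week, should not be adopted. Under the same no-effect 15-day Poisson model its chance-response rate is about 0.6% at 1/week, 11% at 2/week and 35% at 3/week, so it depends on baseline more than the present rule does. It also selects on a noisy baseline and drops patients who entered on other symptoms.

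**Variable I.** Analyse each patient's proportion of stools in a Bristol range specified before analysis, over the same 15 days, adjusted for the baseline proportion.

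**Cost.** Outcome wording and a little analysis work, from the same diaries and visits. The summary is less simple to read than a responder percentage.
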